12.5. Performance of case definition

12.5.1. Primary performance of case definition analysis

12.5.1.1. (PO2) To assess the performance of the LRTI case definition and severity scale for RSV associated cases

Template 20 Comparison between [WHO and GSK – WHO and Nokes – GSK and Nokes, WHO and exploratory] case definitions for RSV-LRTIs, all episodes considered (PPS)

		WHO RSV LRTI case episodes	WHO RSV LRTI case definition, all episodes				
		Case	Non Case				
GSK RSV LRTI case	Case						
definition, all episodes	Non Case						
Total							

Template 21 Measures of agreement between [WHO and GSK – WHO and Nokes – GSK and Nokes, WHO and exploratory] case definitions for RSV-LRTIs, all episodes considered (PPS)

Measures of Agreement	Value	LL	UL
Sensitivity			
Specificity			
Positive predictive value			
Negative predictive value			
Proportion of overall			
agreement			
Cohen's kappa coefficient			

Proportion of overall agreement = proportion of cases similarly classified

Cohen's kappa coefficient = the magnitude of the kappa coefficient represent the proportion of agreement greater than that expected by chance.

LL, UL = 95% Lower and Upper confidence limits

Note

The [first case definition in a pair] is considered as the classification of reference.

Template 22 Comparison between [WHO and GSK – WHO and Nokes – GSK and Nokes – WHO and exploratory] case definitions for RSV severe-LRTIs, all episodes considered (PPS)

		WHO RSV severe-L epi	WHO RSV severe-LRTI case definition, all episodes		
		Case			
GSK RSV severe-	Case				
LRTI case definition, all episodes	Non Case				
Total					

200150 (EPI-RSV-005 BOD)

Statistical Analysis Plan Amendment 1 Final

Template 23 Measures of agreement between [WHO and GSK – WHO and Nokes – GSK and Nokes – WHO and exploratory] case definitions for RSV severe-LRTIs, all episodes considered (PPS)

Measures of Agreement	Value	LL	UL
Sensitivity			
Specificity			
Positive predictive value			
Negative predictive value			
Proportion of overall			
agreement			
Cohen's kappa coefficient			

Proportion of overall agreement = proportion of cases similarly classified

Cohen's kappa coefficient = the magnitude of the kappa coefficient represent the proportion of agreement greater than that expected by chance.

LL, UL = 95% Lower and Upper confidence limits

Note

The [first case definition in a pair] is considered as the classification of reference.

Template 24 Number and percentages of RSV LRTI and RSV severe LRTIs by case definitions and hospitalization status, all episodes considered (PPS)

		Total episodes		Hospitalized			Non-h	ospitali	zed	
Case definitions (all episodes)	Categories	N	n	%	LL	UL	n	%	LL	UL
RSV hospitalization										
WHO	RSV LRTI									
	RSV severe-LRTI									
Nokes	RSVLRTI									
	RSV severe-LRTI									
GSK	RSV LRTI									
	RSV Severe LRTI									
Exploratory	RSV LRTI									
	RSV severe LRTI									
	RSV very severe LRTI									

n= number of episodes by each hospitalization status in each category N= total number of episodes

IN= total number of ep

%=n/N

LL, UL = 95% Lower and Upper confidence limits

Statistical Analysis Plan Amendment 1 Final

Template 25 Comparison between RSV hospitalization and [WHO RSV LRTI hospitalization – Nokes RSV LRTI hospitalization, GSK RSV LRTI hospitalization, RSV LTRI hospitalization (exploratory)], all episodes considered (PPS)

		RSV hospitaliza	tion, all episodes	Total
		Case	Non Case	
[WHO RSV LRTI hospitalization –	Case			
Nokes RSV LRTI hospitalization, GSK RSV LRTI hospitalization], all episodes	Non Case			
Total				

Note:

RSV hospitalization is considered as the classification reference

Template 26 Measures of agreement between RSV hospitalization and [WHO RSV LRTI hospitalization – Nokes RSV LRTI hospitalization, GSK RSV LRTI hospitalization, RSV LRTI hospitalization (exploratory)] all episodes considered (PPS)

Measures of Agreement	Value	LL	UL
Sensitivity			
Specificity			
Positive predictive value			
Negative predictive value			
Proportion of overall			
agreement			
Cohen's kappa coefficient			

Proportion of overall agreement = proportion of cases similarly classified

Cohen's kappa coefficient = the magnitude of the kappa coefficient represent the proportion of agreement greater than that expected by chance.

LL, UL = 95% Lower and Upper confidence limits

Note

RSV hospitalization is considered as the classification of reference.

Template 27 Comparison between RSV hospitalization and [WHO RSV severe LRTI hospitalization – Nokes RSV severe LRTI hospitalization – GSK RSV severe LRTI hospitalization, RSV severe LRTI hospitalization (exploratory] all episodes considered (PPS)

		RSV hospitaliza	Total	
		Case	Non Case	
[WHO RSV severe LRTI hospitalization – Nokes	Case			
RSV severe LRTI hospitalization – GSK RSV severe LRTI hospitalization], all episodes	Non Case			
Total				

200150 (EPI-RSV-005 BOD)

Statistical Analysis Plan Amendment 1 Final

Template 28 Measures of agreement between RSV hospitalization and [WHO RSV severe LRTI hospitalization, Nokes RSV severe LRTI with hospitalization, GSK RSV severe LRTI hospitalization, RSV severe LRTI hospitalization (exploratory)] all episodes considered (PPS)

Measures of Agreement	Value	LL	UL
Sensitivity			
Specificity			
Positive predictive value			
Negative predictive value			
Proportion of overall			
agreement			
Cohen's kappa coefficient			

Proportion of overall agreement = proportion of cases similarly classified

Cohen's kappa coefficient = the magnitude of the kappa coefficient represent the proportion of agreement greater than that expected by chance.

LL, UL = 95% Lower and Upper confidence limits

Note

RSV hospitalization is considered as the classification of reference.

200150 (EPI-RSV-005 BOD)

Statistical Analysis Plan Amendment 1 Final

Template 29 Clinical characteristics of WHO RSV LRTI and WHO RSV severe LRTI detected during the examination visit all cases and cases occurring under age of 6 months (PPS)

			Total N =
Characteristics	Parameters or Categories	n	%
WHO RSV LRTI	RTI and SaO2 \ge 95% and increased respiratory rate		
	RTI and SaO2 < 95% and No increased respiratory rate		
	RTI and SaO2 < 95% and increased respiratory rate		
WHO RSV LRTI (< 6	RTI and SaO2 \ge 95% and increased respiratory rate		
months of age)	RTI and SaO2 < 95% and No increased respiratory rate		
	RTI and SaO2 < 95% and increased respiratory rate		
WHO RSV Severe LRTI	RTI and SaO2 \ge 95% and increased respiratory rate and at least one symptom induced by difficulty breathing ²		
	RTI and $93\% \le SaO2 < 95\%$ and No increased respiratory rate and at least one symptom induced by difficulty breathing		
	RTI and $93\% \le SaO2 < 95\%$ and increased respiratory rate and at least one symptom induced by difficulty breathing ²		
	RTI and SaO2 < 93% and no increased respiratory rate and no symptoms induced by difficulty breathing		
	RTI and SaO2 < 93% and increased respiratory rate and		
	RTI and SaO2 < 93% and No increased respiratory rate and at least one symptom induced by difficulty breathing		
	RTI and SaO2 < 93% and increased respiratory rate and at least one symptom induced by difficulty breathing		
	RTI and SaO2 \ge 95% and increased respiratory rate and at least one symptom induced by difficulty breathing ²		
WHO RSV Severe LRTI (< 6 months of age)	RTI and $93\% \le SaO2 < 95\%$ and No increased respiratory rate and at least one symptom induced by difficulty breathing		
	RTI and 93% \leq SaO2 < 95% and increased respiratory rate and at least one symptom induced by difficulty breathing ²		
	RTI and SaO2 < 93% and no increased respiratory rate and no symptoms induced by difficulty breathing		
	RTI and SaO2 < 93% and increased respiratory rate and no symptoms induced by difficulty breathing		
	RTI and SaO2 < 93% and No increased respiratory rate and at least one symptom induced by difficulty breathing		
	RTI and SaO2 < 93% and increased respiratory rate and at least one symptom induced by difficulty breathing		

RTI = respiratory tract infection

SaO2 = Blood Oxygen Saturation

LRTI= Lower respiratory tract infection

N = total number of episodes

n/% = number / percentage of episodes in a given category

Increase respiratory rate: \geq 60/minute (< 2m of age); \geq 50/minute (2-11m of age); \geq 40/minute (12-24m of age)

Symptoms induced by difficulty breathing: Irritability/agitation, Lethargy/sleepiness, Severe chest in drawing,

Reduced/no vocalization, Apnoea > 20 sec, Cyanosis, Stop feeding well/dehydration

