NOV LIVIT HUSPILAIIZALIUH	Needing the case definition of KSV LK11 and 1s associated with
	nospitalization
RSV severe LRTI*	Infant with RSV LRTI AND
	At least one of the following two
	• $SnO_2 < 90\%$ AND clinical diagnosis of LRTL or
	bronchialitis
	bionchiolius
	• Lower chest wall indrawing

200150 (EPI-RSV-005 BOD) Statistical Analysis Plan Amendment 1 Final

Endpoint	Case definition		
RSV severe LRTI	Meeting the case definition of RSV severe LRTI and is		
hospitalization	associated with hospitalization		
WHO 2015			
RSV LRTI*	Infant with history of cough OR		
	Difficulty breathing ²] AND		
	[SpO ₂ < 95% OR		
	RR increase ³] AND		
	Confirmed RSV infection ⁴		
RSV LRTI hospitalization	Meeting the case definition of RSV LRTI AND		
	associated with hospitalization		
RSV severe LRTI*	Infant with RSV LRTI AND		
	[SpO ₂ < 93%, OR		
	Lower chest wall indrawing]		
RSV severe LRTI	Meeting the case definition of RSV severe-LRTI, AND		
hospitalization*	associated with hospitalization		
LRTI (all cause)	[Infant with history of cough OR		
	Difficulty breathing ²] AND		
	[SpO ₂ < 95% OR PR increase ³]		
Severe LRTT (all cause)			
	[SPO2 < 93%, OR Lower chest wall indrawing]		
Exploratory definitions			
RSV I RTI	[Infant with Couch OR		
	Difficulty breathing AND		
	$[SnO_2 < 95\% OR]$		
	RR increase OR		
	Lower chest wall indrawing] AND		
	Confirmed RSV infection ⁴		
RSV LRTI hospitalization	Meeting the case definition of RSV LRTI AND		
	associated with hospitalization		
RSV severe LRTI	Infant with RSV LRTI AND		
	SpO ₂ < 93%		
RSV severe LRTI	Meeting the case definition of RSV severe-LRTI		
hospitalization	AND		
	associated with hospitalization		
RSV very severe LRTI	Meeting the case definition of RSV LRTI AND SpO ₂ < 90%		
RSV very severe LRTI	Meeting the case definition of RSV very severe-LRTI		
hospitalization	AND		
	associated with hospitalization		

¹Surveillance mechanism not designed to detect cases meeting this endpoint.

² Based on history reported by parents/LARs and includes difficulty breathing associated with nasal obstruction

³ RR defined as ≥ 60/minute (< 2 months of age); ≥ 50/minute (2 to 11 months of age); ≥40/minute (12 to 24 months of age)

⁴RSV infection confirmed on nasal swab positive for RSV A or B by quantitative polymerase chain reaction (qPCR)

⁵RSV sampling and testing is based on medical judgment of medical practitioner or driven by algorithm

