11.2. Standard data derivation

11.2.1. Case definitions

11.2.1.1. Any cause RTI

The subject will be defined as RTI positive when he is presenting one or more of the following items:

- Cough reported in interview during the examination visit or Dica (fields [EXAM VS.SYMP CAT]="Cough" and [EXAM VS.SYMP REP]="Y")
- Runny nose reported in interview during the examination visit or Dica (fields [EXAM_VS.SYMP_CAT]="Runny nose" and [EXAM_VS.SYMP_REP]="Y")
- Blocked nose reported in interview during the examination visit or Dica (fields [EXAM_VS.SYMP_CAT]="Blocked nose" and [EXAM_VS.SYMP_REP]="Y")

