11.2.1.4. LRTI

11.2.1.4.1. Any LRTI (WHO definition)

The subject will be defined as LRTI positive according to WHO definition when he is presenting:

- history of cough or difficulty breathing,
- and a measured oxygen saturation < 95% or an increase of respiratory rate.

200150 (EPI-RSV-005 BOD)

Statistical Analysis Plan Amendment 1 Final

For derivation purposes we are characterizing 2 groups of items:

- Component A which gathers items used to derive history of cough and difficulty breathing,
- Component B which gathers the oxygen saturation and respiratory rate.

Component A:

The subject will be considered positive for Component A when one or several of the following items are reported in interview during the examination visit:

- Cough reported in interview during the examination visit or Dica (fields [EXAM_VS.SYMP_CAT]="Cough" and [EXAM_VS.SYMP_REP]="Y")
- And/or difficulty breathing as defined in section 11.2.2.1

Please note that the 2 symptoms: blocked nose and runny nose are not considered here for the derivation, indeed even if in the table 1 note 1 the case definition mentioned "Based on history reported by parents/LARs and includes difficulty breathing associated with nasal obstruction". (in fact it relates to how the data is intended to be collected in future trials where the mother is asked does the child have difficulty breathing yes or no. It is meant to qualify that if the child's breathing difficulty is due to only blocked nose if the mother says its difficulty breathing it is. However, in this study we don't have the question difficulty breathing and so we cannot know whether the blocked nose was or not associated with difficulty breathing in the mothers view)

Component B:

The subject will be considered positive for Component B when one or both of the following statement is reached:

- Blood Oxygen Saturation <95% (field [CLN_SGN2.BLSAT_V])
- And/or Increased Respiratory rate as defined in section 11.2.2.2

Please note that Blood Oxygen Saturation and respiratory rate are measured during the examination visit.

The subject will be defined as LRTI positive according to WHO definition when he is positive for Component A AND positive for Component B.

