11.2.1.4.2. Severe LRTI (WHO definition)

Severe LRTI status will be defined positive when the subject is LRTI positive (see section 11.2.1.4.1) AND present one or both of the 2 following items:

• Blood Oxygen Saturation <93% (field [CLN_SGN2.BLSAT_V])

Statistical Analysis Plan Amendment 1 Final

• **AND/OR** Any chest indrawing present at examination visit (fields [CLN_SIGN.SIGN_CAT]="Chest indrawing" and [CLN_SIGN.SIGN_YN]="Y")

Please note that the chest indrawing symptom used to define severity is the one measured by the medical team during the examination visit.

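### SAP Template 29 describes WHO RSV LRTI and WHO severe RSV LRTI with sponsor-scale terms, so its rows cannot isolate chest indrawing below 93% saturation and need not sum to the number of WHO episodes

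*SAP*

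**What the plan says.** **WHO LRTI.** SAP 11.2.1.4.1 requires "history of cough or difficulty breathing", "and a measured oxygen saturation < 95% or an increase of respiratory rate". It leaves nasal symptoms out of the entry term: "Please note that the 2 symptoms: blocked nose and runny nose are not considered here for the derivation".

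**WHO severe LRTI.** SAP 11.2.1.4.2 adds either saturation below 93% or "Any chest indrawing present at examination visit". No other sign counts. SAP 11.2.1.7 then defines RSV severe LRTI from this status plus RSV positivity.

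**Template 29.** The title and row groups are WHO RSV LRTI and WHO RSV severe LRTI, for all ages and for infants under 6 months. Every row starts from RTI, which SAP 11.2.1.1 defines by any one of cough, runny nose or blocked nose. Each severe block has seven rows, formed by saturation band, respiratory rate, and presence or absence of a symptom caused by difficulty breathing. The footnote defines such symptoms by a list that begins "Symptoms induced by difficulty breathing: Irritability/agitation, Lethargy/sleepiness, Severe chest in drawing" and goes on to reduced vocalisation, apnoea, cyanosis and poor feeding.

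**Source of the list.** These are the severe-column signs of the sponsor's scale in Protocol Section 4.1, Table 4. SAP 11.2.1.4.4 uses them for the sponsor (GSK) severe definition. SAP Section 9, which lists changes from planned analyses, does not mention applying them to WHO cases.

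**The concern.** A table headed as WHO severe LRTI should break those episodes down by what makes them WHO severe: low saturation, indrawing, or both. Template 29 keeps the WHO saturation cut of 93% but replaces the indrawing criterion with a seven-sign composite. It also replaces the WHO entry symptom with a different one. The pattern suggests terms carried over from a sponsor-definition table.

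The table sits under the co-primary objective on case-definition performance, and a reader would expect it to show how WHO cases met the definition. The exploratory definition in SAP Table 4 moves indrawing from the severe tier into any LRTI, so how often indrawing accompanies low saturation is a natural question to put to this table. As specified, the table cannot answer it, and its rows may leave some WHO episodes uncounted.

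**Working it through.** The plan states no figure on this point, so the check sets the definitions side by side and follows each type of WHO episode to its row.

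**1. Definitions compared**

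| Element | WHO derivation (SAP 11.2.1.4.1–2) | Template 29 severe rows |
|---|---|---|
| Entry symptom | Cough or difficulty breathing | RTI: cough, runny nose or blocked nose |
| Objective finding | SaO2 <95% or raised respiratory rate | Same |
| Severity by saturation | <93% | Same cut |
| Severity by sign | Chest indrawing at examination | Any of seven listed signs |

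**2. How indrawing is coded.** The sponsor scale in the protocol speaks of severe indrawing. SAP 11.2.1.4.4 implements that item as any chest indrawing at the examination visit, with the same field and value as the WHO derivation. On that coding, the composite is indrawing or any of six other signs.

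**3. The three SaO2 ≥93% rows.** A WHO severe episode with SaO2 ≥93% must have indrawing, since it qualifies no other way. It therefore always has at least one listed sign. If it has an RTI symptom it is placed in a row, and the count is right. The label is wrong, because it credits a list of seven signs where one sign is responsible.

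**4. The four SaO2 <93% rows.** Among WHO severe episodes with an RTI symptom and SaO2 <93%, let:
- a = number with indrawing;
- b = number without indrawing but with one of the other six signs;
- d = number with none of the seven.

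The table reports a + b and d, each split by respiratory rate. The WHO breakdown needs a against b + d. From the table, a is known only to lie between 0 and a + b. If c is the total of the three SaO2 ≥93% rows, the number of tabulated severe episodes with indrawing lies anywhere from c to c + a + b.

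**5. The entry term.** Cough, nasal symptom and difficulty breathing, each yes or no, give 8 combinations.
- Cough or difficulty breathing (WHO): 6 combinations.
- Of these 6, also RTI (cough or nasal symptom): 5.
- WHO but not RTI: 1, difficulty breathing alone.

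For each entry combination, count the WHO-severe finding patterns. Indrawing is held at three levels (none, non-severe, severe) and the other six signs as any or none.
- SaO2 <93%: 2 (rate) × 3 (indrawing) × 2 (other signs) = 12.
- SaO2 93 to <95%: 2 × 2 × 2 = 8, because indrawing is required.
- SaO2 ≥95%: 1 × 2 × 2 = 4, because raised rate and indrawing are both required.
- Total: 12 + 8 + 4 = 24.

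WHO-severe patterns number 6 × 24 = 144. With any indrawing counted as a listed sign, 5 × 24 = 120 fall in a row. The remaining 1 × 24 = 24 fall in none, all with difficulty breathing but no cough or nasal symptom. These are logical patterns, not expected patients. The three WHO RSV LRTI rows have the same gap, because they also start from RTI.

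**6. After the fix.** With chest indrawing as the sign and cough or difficulty breathing as the entry term, the seven rows are an exact partition: all 144 patterns fall in one row each, and no pattern that is not WHO severe satisfies a row.

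**The case against.** **Group membership.** WHO severe status is set by SAP 11.2.1.4.2 and 11.2.1.7, and the rows only subdivide that group. This stands. A reader might infer from the labels that an infant with, say, irritability but no indrawing and SaO2 ≥93% would be counted as WHO severe. The documents do not support that, since nothing lets a mock-table footnote override the derivation.

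**Severe versus any indrawing.** A reader might also infer that WHO-severe infants with only non-severe indrawing drop out of the table. Read literally, the footnote would remove the row for 15 more of the 144 patterns (those with an RTI symptom, SaO2 ≥93% and non-severe indrawing only). However, SAP 11.2.1.4.4 codes the sponsor's indrawing item as any indrawing, in the same field as the WHO sign. On that coding the 15 become 0.

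**Rarity of the missing cases.** Protocol Sections 4.1 and 6.5.12 direct examination visits to children with RTI symptoms and suspected difficulty breathing. Difficulty breathing without cough or nasal symptoms is therefore outside the intended pathway. This largely stands, although SAP Section 9 acknowledges examination visits without a surveillance visit, so some such episodes are possible.

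**Purpose of the table.** SAP 6.8.1 does not describe Template 29, and Protocol 9.7.3 plans frequency tables of symptoms and clinical parameters. A wider sign list can therefore be legitimate. That supports showing the seven signs, but not using them as the severity term in rows headed WHO severe.

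**Conclusion.** The point holds as a specification error in one descriptive table. Two defects would reach the output: the four SaO2 <93% rows, in both age blocks, cannot separate indrawing from six signs outside the WHO definition, and WHO episodes with difficulty breathing alone have no row. The three SaO2 ≥93% rows are mainly mislabelled.

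This rests on two readings of the SAP: that the table is restricted to episodes meeting the WHO derivation, and that indrawing is coded as in 11.2.1.4.2 and 11.2.1.4.4. The number of episodes without a row cannot be computed, because the documents give no symptom frequencies. It is probably small, and a claim that a large share of WHO severe cases would be lost has no support in the documents. WHO incidence and agreement estimates use the 11.2.1.4 derivations and do not change.

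**What to change.** In the WHO rows of Template 29:
- replace RTI with cough or difficulty breathing, as derived in 11.2.1.4.1;
- replace the seven-sign term with chest indrawing present at the examination visit, as coded in 11.2.1.4.2;
- add a programmed check that the rows sum to the number of WHO (or WHO severe) episodes in each block.

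If the seven-sign breakdown is wanted, show it in a separate panel labelled as sponsor-scale signs.

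Two neighbouring inconsistencies should be settled separately. SAP Table 4 gives the WHO sign as "Lower chest wall indrawing", whereas 11.2.1.4.2 takes any indrawing. The Template 29 footnote counts respiratory rates at the limit as raised (≥60, ≥50, ≥40), whereas 11.2.2.2 requires rates above it.

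The cost is a template edit and a small programming change on data already collected.

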12.5.2. Tertiary performance of case definition analysis

12.5.2.1. (TO3) To explore the association of RSV viral load with the incidence of RSV-associated RTI, LRTI and/or severe LRTI (as determined by the LRTI case definition and severity scale).

Template 30 Descriptive statistics of total RSV viral load during all RSV episodes classified according to WHO severity scale occurring during the [first year of life - second year of life-2 year follow-up period] by non overlapping disease severity (PPS)

Category	n	Mean	95%	SD	Q1	Median	Q3	Min/Max
			CI					
RSV asymptomatic (Excluding RSV-RTI, WHO RSV-LRTI, WHO RSV-severe LRTI)								
RSV RTI (Excluding WHO RSV-LRTI, WHO RSV-severe LRTI)								
WHO RSV LRTI (Excluding WHO RSV-severe LRTI)								
WHO RSV-severe LRTI								

n= Number of RSV episodes meeting the case definitions (an episode is assigned to a single category based on the highest severity of the symptom experienced).

SD=Standard Deviation

Q1 and Q3 = 1^{st} and 3^{rd} quartiles

Min/Max = Minimum/Maximum

Total RSV viral load computed as RSV A Viral load + RSV B Viral load

Note:

There may have been multiple swabs for an episode. In such cases, the swab with highest viral load was considered for this analysis

Template 31 Descriptive statistics of total RSV viral load during all RSV episodes classified according to WHO severity scale occurring during the [first year of life - second year of life-2 year follow-up period] by overlapping disease severity (PPS)

Category	n	Mean	95% CI	SD	Q1	Median	Q3	Min/Max
RSV asymptomatic								
RSV RTI								
WHO RSV LRTI								
WHO RSV-severe LRTI								

n= Number of RSV episodes meeting the case definitions.

SD=Standard Deviation

Q1 and Q3 = 1st and 3rd quartiles

Min/Max = Minimum/Maximum

Total RSV viral load computed as RSV A Viral load + RSV B Viral load

Note:

200150 (EPI-RSV-005 BOD)

Statistical Analysis Plan Amendment 1 Final

Template 32 Descriptive statistics of total RSV viral load during all RSV hospitalization episodes classified according to WHO severity scale occurring during the [first year of life - second year of life- 2 year follow-up period] by non overlapping disease severity (PPS)

Category	n	Mean	95% CI	SD	Q1	Median	Q3	Min/Max
RSV hospitalization (Excluding WHO RSV LRTI hospitalization, WHO RSV severe LRTI hospitalization)								
WHO RSV LRTI hospitalization (Excluding WHO RSV severe LRTI hospitalization)								
WHO RSV Severe LRTI hospitalization								

n= Number of RSV hospitalization episodes meeting the case definitions (an episode is assigned to a single category based on the highest severity of the symptom experienced).

SD=Standard Deviation

Q1 and Q3 = 1st and 3rd quartiles

Min/Max = Minimum/Maximum

Total RSV viral load computed as RSV A Viral load + RSV B Viral load

Note:

There may have been multiple swabs for an episode. In such cases, the swab with highest viral load was considered for this analysis

Template 33 Descriptive statistics of *total* RSV viral load during all *RSV* hospitalization episodes classified according to WHO severity scale occurring during the [first year of life - second year of life- 2 year follow-up period] by overlapping disease severity (PPS)

Category	n	Mean	95%	SD	Q1	Median	Q3	Min/Max
			CI					
RSV hospitalization								
WHO RSV LRTI hospitalization								
WHO RSV Severe LRTI hospitalization								

n= Number of RSV hospitalization episodes meeting the case definitions

SD=Standard Deviation

Q1 and Q3 = 1st and 3rd quartiles

Min/Max = Minimum/Maximum

Total RSV viral load computed as RSV A Viral load + RSV B Viral load

Note:

200150 (EPI-RSV-005 BOD) Statistical Analysis Plan Amendment 1 Final

Template 34 Incidence rate of first episode of [RSV LRTI (exploratory), RSV severe LRTI (exploratory)], by age interval – overall and by country (PPS)

						95% (exact CI
Country	Age interval (Months)	Total number of subjects	Total number of first episode	Total number of person- years	Incidence rate (100 person- years)	LL	UL
Overall	0-5						
	6-11						
	0-11						
	12-23						
	0-23						
<each country=""></each>							

Incidence rate computed using the number of first episode as numerator and the total number of person-years over the entire follow-up as denominator

CI=confidence interval, LL, UL for incidence = Exact 95% Lower and Upper confidence limits

Template 35 Proportion affected by at least one episode of [RSV LRTI (exploratory), RSV severe LRTI (exploratory)] by age interval – overall and by country (PPS)

					95% e	xact Cl
Country	Age interval (Months)	Total number of subjects at birth	Total number of subjects affected	Proportion affected	LL	UL
Overall	0-5					
	6-11					
	0-11					
	12-23					
	0-23					
<each country=""></each>						

Proportion affected computed using the number of subjects experiencing at least one episode as numerator and the total number of subjects at birth as denominator.

CI=confidence interval, LL, UL for proportion affected = Exact 95% Lower and Upper confidence limits

200150 (EPI-RSV-005 BOD)

Statistical Analysis Plan Amendment 1 Final

Template 36 Descriptive statistics of total RSV viral load during all RSV episodes classified according to exploratory severity scale occurring during the [first year of life - second year of life-2 year follow-up period] by non overlapping disease severity (PPS)

Category	n	Mean	95% Cl	SD	Q1	Median	Q3	Min/Max
Exploratory RSV LRTI (Excluding exploratory RSV- severe LRTI, exploratory RSV very severe LRTI)								
Exploratory RSV-severe LRTI (excluding exploratory RSV very severe LRTI)								
Exploratory RSV very severe LRTI								

n= Number of RSV episodes meeting the case definitions (an episode is assigned to a single category based on the highest severity of the symptom experienced).

SD=Standard Deviation

Q1 and Q3 = 1st and 3rd quartiles

Min/Max = Minimum/Maximum

Total RSV viral load computed as RSV A Viral load + RSV B Viral load Note:

There may have been multiple swabs for an episode. In such cases, the swab with highest viral load was considered for this analysis

Template 37 Descriptive statistics of total RSV viral load during all RSV episodes classified according to exploratory severity scale occurring during the [first year of life - second year of life-2 year follow-up period] by overlapping disease severity (PPS)

Category	n	Mean	95% Cl	SD	Q1	Median	Q3	Min/Max
Exploratory RSV LRTI								
Exploratory RSV-severe LRTI								
Exploratory RSV very severe LRTI								

n= Number of RSV episodes meeting the case definitions.

SD=Standard Deviation

Q1 and Q3 = 1st and 3rd quartiles

Min/Max = Minimum/Maximum

Total RSV viral load computed as RSV A Viral load + RSV B Viral load

Note:

200150 (EPI-RSV-005 BOD)

Statistical Analysis Plan Amendment 1 Final

Template 38 Descriptive statistics of total RSV viral load during all RSV hospitalization episodes classified as according to exploratory severity scale occurring during the [first year of life - second year of life- 2 year follow-up period] by non overlapping disease severity (PPS)

Category	n	Mean	95% Cl	SD	Q1	Median	Q3	Min/Max
Exploratory RSV LRTI hospitalization (Excluding exploratory RSV-severe LRTI hospitalization, exploratory RSV very severe LRTI hospitalization)								
Exploratory RSV-severe LRTI hospitalization (excluding exploratory RSV very severe LRTI hospitalization)								
Exploratory RSV very severe LRTI hospitalization								

n= Number of RSV hospitalization episodes meeting the case definitions (an episode is assigned to a single category based on the highest severity of the symptom experienced).

SD=Standard Deviation

Q1 and Q3 = 1st and 3rd quartiles

Min/Max = Minimum/Maximum

Total RSV viral load computed as RSV A Viral load + RSV B Viral load

Note:

There may have been multiple swabs for an episode. In such cases, the swab with highest viral load was considered for this analysis

Template 39 Descriptive statistics of *total* RSV viral load during all *RSV* hospitalization episodes classified according to exploratory severity scale occurring during the [first year of life - second year of life- 2 year follow-up period] by overlapping disease severity (PPS)

Category	n	Mean	95% Cl	SD	Q1	Median	Q3	Min/Max
Exploratory RSV LRTI hospitalization								
Exploratory RSV-severe LRTI hospitalization								
Exploratory RSV very severe LRTI hospitalization								

n= Number of RSV hospitalization episodes meeting the case definitions

SD=Standard Deviation

Q1 and Q3 = 1^{st} and 3^{rd} quartiles

Min/Max = Minimum/Maximum

Total RSV viral load computed as RSV A Viral load + RSV B Viral load

Note:

